5.2. Fixed Dose

Cohorts (EC3, DEC2, FEC and potentially GEC) shall use a maximum fixed dose of INT230-6 of 175 mL per dosing session with the number of tumors being dosed per session to be decided by the investigators.

Based on preliminary data from the IT-01 study, the ratio of length to width to height is very consistent across the first 200+ tumors that we have volumetric based dosing using the modified ellipsoid formula. We have used this data to simplify the dosing based on the longest diameter measurement alone. The dose of INT230-6 will be calculated using the algorithm in Table 8.

Table 8: INT230-6 Dosing calculations

[REDACTED]	[REDACTED]	[REDACTED]	[REDACTED]	[REDACTED]
[REDACTED]	[REDACTED]	[REDACTED]	[REDACTED]	[REDACTED]
[REDACTED]				
[REDACTED]				
[REDACTED]				

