7.5. Examination of Subgroups

Analysis endpoints of safety and efficacy variables may be further explored with the following subgroups:

- Tumor ratio (1:4, 1:3, 1:2 or dose set by longest diameter formulas)
- Dose schedule (every 2 weeks versus every 4 weeks)
- Superficial tumor injection subjects versus deep tumor injection subjects
- Tumor type (Sarcoma)
- Status of prior treatment with platinum-based antineoplastics or vinca alkaloid therapies
- Subjects with less than 2 tumors injected compared to those with ≥ 2 tumors
- Tumor burden: subjects receiving $\geq 40\%$ of tumor burden injected versus those receiving $< 40\%$; tumor burden is calculated based on EDC documentation of target, bystander, non-target, and new tumors. Subjects receiving $\geq 40\%$ of baseline total tumor burden injected overall (during the course of therapy) and at first dose will be explored. For overall, the sum of all injection volumes will be used in the calculation.

The subgroups to be analyzed for each endpoint are described in Section 8, Section 9, and Section 10.

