1. TOTAL TUMOR BURDEN (TTB)

Step 1: If all 3 dimensions are reported, volume = (longest*shortest*depth*0.63)

Step 2: If not all 3 dimensions are reported and longest diameter is reported, volume calculation is based on the longest diameter measurement.

1. If $. < \text{longest} < 1.5 \text{ cm}$, volume = 1 cm^3
2. If $1.5 \leq \text{longest} \leq 4 \text{ cm}$, volume = $\text{longest}^3/2$
3. If $4 < \text{longest} < 9 \text{ cm}$, volume = $\text{longest}^3/3$
4. If $\text{longest} \geq 9 \text{ cm}$, volume = $\text{longest}^3/4$
5. If shortest is only measurement reported, Diameter = shortest and follow step 2 tasks 1 to 4 for volume calculations

Step 3: Sum all calculated volume values across target and bystander tumors.

2. % DOSED TTB

Step 1. Calculate TTB of all of a patient's bystander and target tumors reported in the database using the TTB formulas above.

Step 2. Calculate patient's cumulative dose of INT230-6

Step 3. Calculate % Dosed TTB as (cumulative dose / Patient TTB) * 100.

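### For tumors without all three dimensions, the SAP's fallback volume rule drops by 33% just above 4 cm and by 25% at 9 cm, so a 1 mm difference can change a subject's 40% group in exploratory survival curves

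*SAP*

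**What the plan says.** SAP Appendix 1, item 1 (Total Tumor Burden), has two routes to a tumor's volume. With all three dimensions, Step 1 multiplies them together and by 0.63. Otherwise, where a longest diameter is available, Step 2 applies: "volume calculation is based on the longest diameter measurement". Step 2 has four brackets for longest diameter L:

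- under 1.5 cm: fixed at 1 cc
- 1.5 cm to 4 cm inclusive: L³/2
- above 4 cm and below 9 cm: L³/3
- 9 cm and above: L³/4

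If only the shortest diameter is reported, it is used in place of L. Volumes are summed over target and bystander tumors to give TTB. Item 2 defines the percentage dosed as cumulative INT230-6 dose over TTB, times 100.

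The percentage is cut at 40% in three places. SAP 9.2 uses it in three of its six bullets of Kaplan-Meier overall survival curves, each shown for three populations, and hazard ratios between curves are possible. SAP 7.5 uses it as a subgroup, both at first dose and over the whole course; on the latter it says "For overall, the sum of all injection volumes will be used in the calculation". SAP 9.1 lists the category for each subject.

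The SAP gives no reason for changing the divisor with size and no sensitivity analysis of the 40% cut. Protocol 5.2 supports dosing by longest diameter with the statement that "the ratio of length to width to height is very consistent across the first 200+ tumors".

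**The concern.** A volume rule should not give a larger tumor a smaller volume, yet Step 2 does so on crossing 4 cm and again at 9 cm. Because TTB is a denominator, a drop in assigned volume raises the percentage dosed. For a fixed dose, crossing a breakpoint upward can therefore move a subject only from below 40% to 40% or above.

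At stake is who sits on which survival curve. SAP 2 and 3.1 tie the research hypothesis to treating enough of the tumor burden, and the 40% split is how that idea is displayed. A group boundary that turns on 1 mm of diameter, through an arithmetic step with no stated rationale, makes those curves harder to interpret. The protocol's remark about consistent tumor shape also sits awkwardly with three divisors.

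**Working it through.** **Reproducing the SAP's example.** The hypothetical patient at the end of Appendix 1 has four tumors with all dimensions: 22.68 + 1.89 + 1.26 + 1.134 = 26.964 cc, as stated. Then 22/26.964 = 81.6%, against the SAP's approximate 81.5%. (The text gives 1 mL for the second tumor but the formula uses 2 mL; 21/26.964 = 77.9%. That is a separate slip.) The example uses Step 1 only, so it never exercises Step 2.

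**Size of the steps** (brackets from Appendix 1, item 1, Step 2).

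| | Below or at breakpoint | Above or at breakpoint | Change | Regained at |
|---|---|---|---|---|
| 4 cm | 4³/2 = 32.0 cc | limit 4³/3 = 21.33 cc | −33.3% | L = 96^(1/3) = 4.58 cm |
| 9 cm | limit 9³/3 = 243.0 cc | 9³/4 = 182.25 cc | −25.0% | L = 972^(1/3) = 9.91 cm |

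At 1.5 cm the rule jumps upward, from 1 cc to 1.5³/2 = 1.69 cc. That is discontinuous but not an inversion.

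**Contrast with Step 1.** The example's first tumor, 4 × 3 × 3 cm, is 22.68 cc by Step 1. With depth missing, Step 2 would give 32.0 cc. A 4.1 cm tumor gets 4.1³/3 = 22.97 cc.

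**Effect on the 40% group, one tumor, dose fixed at 10 mL.**

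- 4.0 cm: 10/32.0 = 31.3%
- 4.1 cm: 10/22.97 = 43.5%
- 4.2 cm: 10/24.70 = 40.5%
- 4.5 cm: 10/30.38 = 32.9%

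The group changes and changes back within half a centimeter.

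**Doses that flip.** A subject flips if the dose lies between 40% of the smaller and 40% of the larger TTB.

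- At the 4 cm limit: 0.4 × 21.33 = 8.53 mL to just under 0.4 × 32.0 = 12.8 mL.
- At the 9 cm limit: 0.4 × 182.25 = 72.9 mL to just under 0.4 × 243 = 97.2 mL. For instance, 80 mL is 34.0% at 8.9 cm and 43.9% at 9.0 cm.

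**Dilution by other tumors.** With 30 cc elsewhere, going from 4.0 to 4.1 cm flips for 0.4 × 52.97 = 21.2 mL to just under 0.4 × 62.0 = 24.8 mL. On the 4.0 cm reading the subject must then already be at 21.19/62.0 = 34.2% or more, compared with 9.19/32.0 = 28.7% for a lone tumor.

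**Implied shape.** Under the 0.63 formula, a divisor k implies (shortest × depth)/L² = 1/(0.63k): 0.79, 0.53 and 0.40 for k = 2, 3 and 4.

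**The case against.** The strongest reply is that the example holds the dose fixed. Protocol Table 8, the longest-diameter dosing rule, is redacted. If it uses the same brackets, dose and assigned volume fall together. At the 1:3 ratio in Protocol 5.2.1, one full session is then 33.3% of a lone tumor on either side of 4 cm, and two are 66.7%. The dose is also cumulative, Protocol 5.5 aims at two or three injections per tumor, and 10 mL is less than one full 1:3 session for 32 cc (10.7 mL). The flip window thus describes a lightly treated subject.

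This stands in part: shared brackets would make flips fewer. It cannot cover everyone. Protocol 3.9 places longest-diameter dosing in Amendment 6; earlier doses used ellipsoid volume, and the escalation cohorts had volume caps. Bystander tumors count in TTB without having been injected. The first-dose version of the subgroup gains nothing from repeat sessions.

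Three stronger readings are tempting but unsupported:

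- That larger tumors generally get smaller volumes. The inversion is local: just over 4 to 4.58 cm, and 9 to about 9.9 cm.
- That the protocol contradicts the SAP on shape. The consistency statement introduces a table that cannot be read, and rising divisors could reflect larger tumors being flatter. A gradual change in shape would still not explain an abrupt fall in volume.
- That the trial's main results are at risk. Survival is an exploratory objective (Protocol 4.4), and neither the safety endpoint nor disease control in the full populations uses TTB.

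**Conclusion.** The defect holds as a discontinuity, with local inversion, in a fallback rule that feeds exploratory groupings. The drops of 33.3% and 25.0% follow exactly from the written brackets. A reclassification by 1 mm follows for a fixed cumulative dose within the windows shown.

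The number of subjects who would change group is unknown. The documents do not say how many tumors lack a dimension, how many of those lie near 4 or 9 cm, or whether dosing shared the brackets. A reader might infer that the 40% survival comparison is materially distorted; the documents do not support that, and the count may be zero. The correction is still worth making, because the rule gives volumes that cannot be right near the breakpoints and the count is easy to obtain.

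**What to change.** For the TTB analysis variable only:

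1. Replace the step in Step 2 with a continuous, increasing function of longest diameter, calibrated on the trial's own tumors with all three dimensions. A regression of log volume on log longest diameter would serve. It does not force one shape constant across sizes, and a positive slope makes it monotone. State the back-transformation.
2. State how tumors under 1.5 cm are handled, since the fixed 1 cc bracket would otherwise disappear or leave its own jump.
3. Rerun the 40% classification and report how many subjects change group.
4. Show the survival curves under the current step rule as a sensitivity analysis.

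The cost is some Appendix 1 wording, a few lines of code and a small amount of extra output, with no new data. One drawback is that TTB may no longer match any longest-diameter formula used for dosing. No change to dosing is proposed.

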5.2.1. E. SUPERFICAL and/or DEEP TUMORS (cohort EC3) Monotherapy of INT230-6

This cohort has simplified the dosing to inject up to the 175mL total dose of INT230-6 into a subject's tumors at each treatment (5 total for induction) session. There is 1 mL of INT230-6 dosed for each 3 cc of tumor volume (1:3) ratio with an induction dosing of 1 doses every 2 weeks for 5 doses with maximum fixed total dose of 175 mL with a maintenance dose of the same maximum of 175 mL given Q9 weeks +/- 10 days. Each tumor should receive up to its

maximum dose to achieve the 1:3 target ratio. The total dose is to be divided up and injected into as many tumors as feasible, with the aim to treat as many visible tumors as possible 1 to 3 times during the course of the induction treatment. After the 5 doses, subjects continue to the maintenance phase where they can repeat injecting new lesions or previously injected lesions with up to 175mL once every 9 weeks. Treatment should continue until patient's tumors disappear (CR), confirmed progression (iCPD) or 2 years whichever is first.

5.2.2. DEC2 Cohorts. COMBINATION WITH ANTI-PD-1 agent(s): see Supplement A for details on each PD-1 agent.

DEC cohorts were initiated and are a combination of INT230-6 plus an anti-PD-1 therapy. The subject population (tumor types) and other details for this group of subjects is defined in Supplement A.

5.2.3. FEC Cohorts. COMBINATION WITH ANTI-CTLA4 agent(s): see Supplement B for protocol details for INT230-6 combinations with anti-CTLA-4 agent(s).

Cohort FEC was initiated and is a combination of INT230-6 plus an anti-CTLA4 therapy. The subject population (tumor types) and other details for this group of subjects is defined in Supplement B.

5.2.4. GEC Cohorts. Cohorts containing the letter “G” dose INT230-6 with agents other than PD-(L)1 or CTLA-4 antibodies.

The subject population (tumor types) and other details for this potential group of subjects will be defined in a future Supplement C.

Study Steering Committee

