3. STUDY OBJECTIVES AND ENDPOINTS

3.1. Research Hypothesis

INT230-6 when administered intratumorally (IT) to one or more tumors at an optimal dose to tumor volume ratio (i.e., greater than 1 mL per 4 cc of tumor) while treating a sufficient amount of the visible disease will safely reduce tumor burden, stabilize disease, promote an immune response against the cancer, and extend overall survival.

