8.4. Dosing and Extent of Exposure

The dose of INT230-6 administered to subjects will be summarized by total dose injected (mL), maximum dose injected into any one tumor (mL), number of tumors injected for each cohort and percent of total tumor burden injected. Drug leakage will also be listed. Subjects receiving study drug per protocol, subjects receiving partial or incomplete drug dose, and reasons for interruption will be summarized. Individual study drug administration records and deviations in administration will be listed, as well as the largest dose into any one tumor.

Pembrolizumab and ipilimumab administration will be summarized in a table and listing and will include total dose administered, dosing delays, reason for dosing delays, number and reasons of subjects permanently discontinuing drug, and number and reasons of infusion interruptions.

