9.2. Progression-Free Survival and Overall Survival

Progression free survival (PFS) and Overall Survival (OS) will be evaluated for the All Treated Population, the REP, and the SEP. PFS will be defined as the time (in months) from first dose of INT230-6 to either observation of clinical deterioration, removal from study, or occurrence of death due to any cause within 126 days (approximately 2 time intervals for tumor assessments) of the last tumor assessment. Progression date will be defined as the end of treatment date as captured per eCRF guidelines when the reason for end of treatment is either 'Radiographic

deterioration' or 'Clinical deterioration.' In subjects without a progression date or with a death date more than 126 days after the last tumor assessment, the PFS time will be censored on the date of last tumor assessment or last treatment date if the subject has no post-baseline tumor assessments. PFS analyses will consider tumor assessments after treatment discontinuation.

OS will be defined as the time (in months) from first dose of INT230-6 to death. Subjects for whom death is not reported will be censored at the date of end of study.

PFS and OS will be summarized in a listing. The median time to OS as obtained from Kaplan-Meier methods will be tabulated by subgroup and will include the median, 25th percentile, 75th percentile, and a 2-sided point-wise 95% confidence interval. Hazard ratios may be determined between certain curves for the Kaplan Meier figures noted below.

A Kaplan Meier figure of OS for the All Treated, REP, and SEP populations will be presented for each of the following:

- a curve all treated monotherapy patients, a curve for subjects that received a dose to total tumor burden < 40% of tumor burden, a curve for those subjects that had a dose to total tumor burden \geq 40%,
- a curve for escalation cohort combining A1, B1, EA, EC, and a curve for escalation cohort combining EC2 and EC3,
- a curve for sarcoma patients in the monotherapy cohort and a curve for monotherapy sarcoma patients having \geq 40% of their total tumor burden treated,
- a curve for the pembrolizumab DEC/DEC2 combined cohort for subjects,
- a curve for all ipilimumab FEC cohort subjects,
- a curve for the ipilimumab FEC sarcoma subjects, a curve for all monotherapy sarcoma patients and a curve for monotherapy sarcoma subjects having \geq 40% of their total tumor burden treated will be included.

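### The SAP labels a drug-to-tumor volume ratio as tumor burden injected or treated, and its 40% cut at first dose lies above the nominal one-session ceiling in every cohort except EC

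*SAP*

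**What the plan says.** SAP Appendix 1, item 1 builds the denominator: "Step 3: Sum all calculated volume values across target and bystander tumors". Item 2 gives the score: "Step 3. Calculate % Dosed TTB as (cumulative dose / Patient TTB) * 100". Section 7.5 confirms the numerator: "For overall, the sum of all injection volumes will be used in the calculation". It also plans a first-dose version, in which subjects receiving at least 40% "of baseline total tumor burden injected overall (during the course of therapy) and at first dose will be explored". Appendix 1 defines only the cumulative version.

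The SAP describes the result in two ways:

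- **As a share of disease.** Section 7.5 speaks of burden injected. Section 8.4 will summarize "number of tumors injected for each cohort and percent of total tumor burden injected". The sarcoma curves in section 9.2 are for subjects with at least 40% "of their total tumor burden treated".
- **As a dose ratio.** The Synopsis (Efficacy Analyses) and the first bullet of section 9.2 describe dose volume relative to total tumor burden.

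The research hypothesis in section 3.1 has two separate conditions: a drug-to-tumor volume ratio, and giving it "while treating a sufficient amount of the visible disease will safely reduce tumor burden".

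**The concern.** The second condition of the hypothesis is about coverage, meaning how much of the visible disease received drug. No variable in Appendix 1 measures that. The 40% variable moves with three things at once: the cohort's drug ratio, the number of sessions, and the share of burden injected. The monotherapy overall survival (OS) curves in section 9.2 pool cohorts at 1:4, 1:3 and 1:2, so two subjects with the same coverage can fall on opposite sides of the cut.

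A reader who sees a curve labelled as at least 40% of burden treated will take it to mean that at least 40% of the disease was injected. The score does not show that. The first-dose version matters as well, because it is the only version fixed when OS time starts, and the nominal ratios leave it few subjects to classify as 40% or more.

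**Working it through.** **1. The SAP's own example** (notes at the end of Appendix 1). Volumes by longest × shortest × depth × 0.63 are 22.68, 1.89, 1.26 and 1.134, so TTB = 26.964 cc. The printed expression gives (20 + 2)/26.964 = 81.6%, which agrees with the stated value of about 81.5%. The sentence itself names 20 mL and 1 mL, which would give 21/26.964 = 77.9%, so the example disagrees with itself on the second tumor. Coverage for the same patient, with both targets injected, is (22.68 + 1.89)/26.964 = 91.1%. The score and the share of disease injected are different quantities.

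**2. Nominal ratios** (SAP Table 3). These are 1:4 in A1, B1 and EA; 1:3 in EC2, DEC, EC3, DEC2 and FEC; and 1:2 in EC. They are maxima per tumor: for EC3, Protocol 5.2.1 refers to the "maximum dose to achieve the 1:3 target ratio".

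**3. Formula.** If a share f of TTB is injected k times at the full ratio 1:r, the score is 100 × k × f / r. The share needed to score 40% is therefore 40% × r / k:

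| Ratio | k = 1 | k = 2 | k = 3 | k = 5 |
|---|---|---|---|---|
| 1:4 | 160% (not possible) | 80% | 53% | 32% |
| 1:3 | 120% (not possible) | 60% | 40% | 24% |
| 1:2 | 80% | 40% | 27% | 16% |

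At 1:3, f = 100% and k = 1 gives 33.3%, classed below 40%. With f = 24% and k = 5 the score is 40%, classed as 40% or more with 76% of the burden never injected. Five full sessions on all tumors would score 125% (1:4), 167% (1:3) or 250% (1:2). A share of disease cannot exceed 100%.

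**4. First dose** (k = 1, taking the score as first-dose mL over baseline TTB). With every tumor fully injected the ceilings are 25%, 33.3% and 50%. Only EC can exceed 40%, and it needs f of at least 80%. Protocol Table 7a caps EC dose 1 at 30 mL in total, so TTB must be at most 30/0.40 = 75 cc. It also caps any one tumor at 15 mL, so a subject with a single tumor needs TTB of at most 15/0.40 = 37.5 cc.

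**5. Dosing by longest diameter.** Protocol 5.2 sets the dose in EC3, DEC2 and FEC from longest diameter; Table 8 is redacted. Assume, for illustration, that it doses at 1:3 of the longest-diameter volumes in Appendix 1, item 1. The example patient's volumes become 32, 4, 4 and 1.6875 cc, and the doses 10.67, 1.33, 1.33 and 0.56 mL. Against the three-dimension TTB of 26.964 cc, the first-dose score is 12.0/26.964 = 44.5% (two targets) or 13.9/26.964 = 51.5% (all four tumors). If dose and TTB use the same volumes (sum 41.6875 cc), the scores are 28.8% and 33.3%. The excess over 33.3% comes entirely from using different volume formulas for dose and burden.

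**The case against.** The best defense is that a dose-to-burden ratio is a legitimate exposure measure and openly part of the plan. SAP section 2 frames the hypothesis as sufficient loading relative to total tumor burden, the Synopsis and the first bullet of section 9.2 describe the split as dose volume against burden, and the calculation is fully specified with an example. That stands: the ratio should be kept. It does not justify the other label.

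Four further points stand as limits on the finding:

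- **The ratios are ceilings.** A reader might infer that drug volume is a fixed fraction of tumor volume. It is not: the note to Protocol Tables 7a and 7b allows lower ratios when volume caps bind, and Protocol 8.10 says less drug is given as tumors shrink.
- **Five full injections of one tumor is an upper case.** Protocol 5.2.1 aims at one to three treatments per tumor in induction, and Protocol 5.5 refers further treatment after three full injections to the Medical Monitor. At 1:3 with three full injections, the coverage needed is exactly 40%. Maintenance can add injections, but the documents do not show how many subjects would be misclassified.
- **The first-dose group is not shown to be empty.** A reader might infer that it must be, outside EC. With Table 8 redacted, that cannot be established for EC3, DEC2 and FEC.
- **Coverage has its own distortion.** It ignores dose per tumor. Under A1's 5 mL first-dose cap, a single 180 cc tumor given 5 mL has 100% coverage at a ratio of 2.8%. Coverage therefore cannot replace the ratio.

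Finally, OS is exploratory, the study is non-randomized, hazard ratios are optional, and no figure in section 9.2 uses the first-dose split.

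**Conclusion.** The concern holds as a labelling and definition fault. % Dosed TTB is a dose-to-burden ratio; outputs that call it burden injected or treated invite a wrong reading. At nominal ratios and up to five full injections, a score of 40% can correspond to coverage from 16% (1:2, five injections) to 80% (1:2 once, or 1:4 twice). Complete coverage in a single session at 1:3 or 1:4 still falls below the cut. This range is what the formula permits, not an estimate of what occurred.

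At first dose, the 40% cut is above the nominal ceiling everywhere except EC, where it needs at least 80% of TTB injected and TTB of at most 75 cc (37.5 cc with one tumor). Scores above 40% in cohorts dosed by longest diameter could come only from a mismatch between dosing and TTB volumes, and would not indicate greater coverage.

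These results assume doses at or below the nominal ratio, the same volume formula for dose and burden except where stated, and a first-dose score of first-dose mL over baseline TTB. They do not support discarding the ratio, nor treating the OS curves as a formal test of the hypothesis: the plan specifies no such test.

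**What to change.** 1. Name the metric 'dose-to-burden ratio' in sections 7.5, 8.4 and 9.2, Appendix 1 and all table and figure titles. Do not describe it as percent of burden injected or treated.
2. Add to Appendix 1 a supplementary coverage variable: baseline volume of tumors injected at least once, divided by baseline TTB, each tumor counted once, maximum 100%. Derive it at first dose and overall, and report it beside the ratio in the 40% subgroup and OS outputs.
3. For the first-dose subgroup, use coverage or drop the 40% ratio cut, and write the chosen definition into Appendix 1.
4. While editing, reconcile the second tumor's dose in the worked example. Also reconcile the tumors that count toward burden: section 7.5 lists target, bystander, non-target and new tumors, while Appendix 1 lists target and bystander only.

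The cost is one derived variable from injection records and tumor measurements that the SAP already plans to list, plus relabelled outputs. Because coverage ignores dose per tumor, the two variables must be read together. Any version classified after first dose remains descriptive for OS, because group membership then depends on what happens after OS time has started. No dose, ratio or clinical rule changes.
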